11.2 Confirmed response

In order to be classified as a hematologic response, confirmation of serum M- protein, serum immunoglobulin free light chain (when primary determinant of response) and urine M- protein (when primary determinant of response) results must be made by verification on two consecutive determinations.

- Bone marrow aspirate and biopsy are **only** required to document CR or sCR, except for patients with evaluable disease **only**, where a bone marrow is required to document all response categories including progression. However, a second confirmatory bone marrow is **not** required to confirm response in any case.
- Radiographic studies are not required to satisfy these response requirements; however, if radiographic studies were performed there should be no evidence of progressive or new bone lesions.

11.3 Bone progression

Caution must be exercised to avoid rating progression on the basis of variation of radiologic technique alone. Compression fracture does not exclude continued response and may not indicate progression. When progression is based on skeletal disease alone, it should be discussed with the Study Chair before removing the patient from the study.

11.4 Response and Progression

Criteria for response and progression are listed in Table 11.5. Progressive disease for all patients as defined in Table 11.5.

Table 11.5

STANDARD IMWG RESPONSE CATEGORY	RESPONSE CRITERIA ^a
Stringent Complete Response (sCR) ^b	
CR as defined plus
 
Normal FLC ratio and
 
 • Absence of clonal PCs by immunohistochemistry or 2- to 4- color flow cytometryⁱ
Complete Response (CR) ^b	
 • Negative immunofixation of serum and urine^c and • Disappearance of any soft tissue plasmacytoma and • <5% PCs in Bone Marrow and • If the only measurable disease is FLC, a normal FLC ratio^d • For patients with extramedullary plasmacytoma present at baseline: a) FDG-avid or PET positive prior to therapy: Mass of any size permitted if PET negative and b) Variably FDG-avid or PET negative: Regression to normal size on CT. For patients with only skin involvement, these same criteria apply to skin lesions measured with a ruler.
Very Good Partial Response (VGPR)	
 • Serum and urine M-protein detectable by immunofixation but not on electrophoresis^c or • ≥90% reduction in serum M-protein and urine M-protein <100 mg/24 h^c • If the only measurable disease is FLC, a >90% reduction in the difference between involved and uninvolved FLC levels • Not applicable for those patients who do not have a “measurable” serum M-spike, serum free light chain, or urine M-spike at baseline
Partial Response (PR)	
 • If present at baseline, ≥ 50% reduction of serum M-protein and reduction in 24-hour urinary M-protein by ≥90% or to <200 mg/24hrs^c • If the only measurable disease is FLC, a ≥50% reduction in the difference between involved and uninvolved FLC levels • If the only measurable disease is BM, a ≥ 50% reduction in BM PCs (provided the baseline PCs was ≥ 30%)

	
 • If present at baseline, $\geq 50\%$ reduction in the size (SPD) of soft tissue plasmacytomas ^j • For patients with extramedullary plasmacytoma present at baseline: $\geq 50\%$ decrease in SPD of up to 6 largest dominant masses and a) FDG-avid or PET positive prior to therapy: one or more PET positive at previously involved sites OR b) Variably FDG-avid or PET negative: regression on CT or by measurements with a ruler in patients with only skin involvement
Minimal Response (MR)	
 • If present at baseline, $\geq 25\%$ but $\leq 49\%$ reduction of serum M protein and reduction in 24-hour urine M-protein by 50-89% which still exceeds 200mg/24 hours ^c and • If present at baseline, $\geq 25\%$ reduction in the size (SPD) of soft tissue plasmacytoma ^j
Stable Disease (SD)	
 • Not meeting criteria for sCR, CR, VGPR, PR, MR or PD
Progressive Disease (PD) ^{b, h}	
Increase of 25% from lowest value in any of the following ^{f, g}:
 
 • Serum M-protein (absolute increase must be ≥ 0.5 g/dL) and/or • Urine M-protein (absolute increase must be ≥ 200 mg/24 hrs) and/or • If the only measurable disease is FLC, the difference between involved and uninvolved FLC levels (absolute increase must be >10 mg/dL) and/or • If the only measurable disease is BM, bone marrow PC percentage (absolute increase must be $\geq 10\%$) ^e • Appearance of a new lesion(s), $\geq 50\%$ increase from nadir in SPD of more than one lesion, or $\geq 50\%$ increase in longest diameter of a previous lesion >1 cm in short axis. Lesions PET positive if PET positive prior to therapy 
Or any one or more of the following:
 
 • Development of new bone lesion or soft tissue plasmacytoma or $\geq 50\%$ increase from nadir in the size (SPD) of existing bone lesions or soft tissue plasmacytoma or $\geq 50\%$ increase in the longest diameter of a previous lesion >1 cm in short axis ^j • 50% increase in circulating plasma cells (minimum of 200 cells per L) if this is the only measure of disease

Clinical Relapse	
One or more of the following direct indicators of increasing disease and/or end-organ dysfunction that are considered related to the underlying plasma cell proliferative disorder:
 
 1. Development of new soft tissue plasmacytomas or bone lesions on skeletal survey, magnetic resonance imaging, or other imaging 2. Definite increase in the size of existing plasmacytomas or bone lesions. A definite increase is defined as a 50% (and at least 1 cm) increase as measured serially by the sum of the products of the cross-diameters of the measurable lesion 3. Hypercalcemia ($>11.5 \text{ mg/dL}$; $>2.875 \text{ mM/L}$) 4. Decrease in hemoglobin of more than 2 g/dL (1.25 mM) or to less than 10 g/dL 5. Rise in serum creatinine by more than or equal to 2 mg/dL ($\geq 177 \text{ mM/L}$) 6. Hyperviscosity
------------------	---

^a All response categories require two consecutive assessments (sCR, CR, VGPR, PR, MR, PD) made at any time before the institution of any new therapy. sCR, CR, VGPR, PR, MR and SD categories require no known evidence of progressive or new bone lesions or extramedullary plasmacytomas if radiographic studies were performed. However, radiographic studies are not required to satisfy these response requirements. Bone marrow assessments need not be confirmed. Each category, except for stable disease, will have a working subcategory of "unconfirmed" [prefix 'u'] to designate first time point at which response category MAY have been achieved if confirmed. The date of the initial test is considered as the date of response for evaluation of time dependent outcomes such as duration of response.

^b CR patient will need to progress at the same level as VGPR and PR patients to be considered a PD. A positive immunofixation alone is not sufficient.

^c If more than one M protein spike meets the criteria for measurable disease at baseline, then both need to be followed for response. Otherwise, only follow the measurable M protein spike for response.

^d In patients in whom the only measurable disease is by serum FLC levels: CR in such patients indicates a normal FLC ratio of 0.26-1.65 in addition to the CR criteria listed above.

^e Bone marrow criteria for PD are only to be used in patients without measurable disease by M protein and by FLC;

^f A "25% increase" refers to M protein, FLC and bone marrow results and does not refer to bone lesions, soft tissue plasmacytoma or hypercalcemia. The lowest value does not need to be a confirmed value. If the lowest serum M-protein is $\geq 5 \text{ g/dL}$, an increase in serum M-protein of $\geq 1 \text{ g/dL}$ is sufficient to define disease progression.

^g In the case where a value is felt to be a spurious result per physician discretion (for example, a possible lab error), that value will not be considered when determining the lowest value.

^h Progressive disease should be confirmed on two consecutive evaluations, where the timing of confirmation is per the treating physician and can be done immediately within the same cycle or on the next cycle. However, treatment may be discontinued for progressive disease that is unconfirmed per physician discretion. In this case, an objective status of PD should be entered on the measurement form and progressive disease should be reported on the event monitoring form.

ⁱ Presence/absence of clonal cells is based upon the k/l ratio. An abnormal k/l ratio by immunohistochemistry requires a minimum of 100 plasma cells for analysis. An abnormal ratio reflecting presence of an abnormal clone is k/l of 4:1 or 1:2.

^j Plasmacytoma measurements should be taken from the CT portion of the PET/CT, or MRI scans, or dedicated CT scans where applicable. For patients with only skin involvement, skin lesions should be measured with a ruler. Measurement of tumor size will be determined by the sum of the products of the maximal perpendicular diameters of measured lesions (SPD).

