4.0 Test Schedule

Tests and procedures	Active Monitoring Phase					
	Prior to registration		Prior to Day 1 Cycle 1	Prior to Day 1 Cycle 2	Prior to Day 1 Cycles 3-6	End of Treatment
	≤28 days	≤14 days				
Window				±3 days	±3 days	±7 days
Complete Medical History		X				
Physical exam, Wt, PS		X	X ³	X	X	X
Adverse event assessment		X		X	X	X
Pregnancy test ¹		X				
Height		X				
Hematology group: CBC with 5-part differential		X	X ³	X	X	X
Chemistry group to include serum creatinine, calcium, T.Bili, D. bili, AST, and ALT		X	X ³	X	X	X
LDH, Beta-2-microglobulin, Plasma cell assessment		X	X ³			
PT/PTT/INR		X				
TSH		X				
Electrophoresis of serum and urine		X	X ^{3,5}	X ⁵	X ⁵	X ⁵
Immunofixation or mass fixation of serum and urine		X		X ⁷	X ⁷	X ⁷
Affected Serum Immunoglobulin ²		X	X ³	X	X	X
Serum Immunoglobulin free light chain		X	X ³	X	X	X
WBLDCT ³ or PET/CT	X			X ³	X ³	
Bone marrow aspirate and biopsy	X					
Patient Medication Diary (Appendix II)			X	X	X	
Research bone marrow sample ^R	X			X ⁶		X ⁴
Research blood sample ^R	X			X ⁶		X ⁴

Cycle 1 = 21

Cycles 2-6 = 28 days

Footnotes on following page:

1. For women of childbearing potential only. Must be done ≤ 7 days prior to registration. If the urine test is positive or cannot be confirmed as negative, a serum pregnancy test will be required
2. Affected immunoglobulin refers to the baseline M-protein type, that is, IgG, IgA, or IgD. Not applicable if patient “non-secretory” or if patient has no heavy chain, i.e. light chain myeloma. Affected immunoglobulin is required after baseline only if it used for disease monitoring instead of SPEP (e.g. IgA myeloma).
3. Baseline then only if clinically indicated.
4. Optional BM sample submission for patients who discontinue treatment due to disease progression or relapse, intolerable AEs, patient refusal, subsequent treatment for myeloma.
5. Urine Electrophoresis required only if used to assess disease response
6. Bone marrow aspirate done at the end of Cycle 1 (prior to cycle 2) will be paid for by research.
7. Immunofixation (IF) only needed in absence of M-Spike to document CR or SCR

R Collected as part of the IRB# 521-93, IRB# 14-009163 and/or IRB# 919-04

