7.3 End of study

All patients in Cohort A, Cohort B, Cohort C and Cohort D enrolled on this clinical trial will be treated on this study only for 6 cycles from the time of registration. After this time, they will no longer be part of the study and will be taken off study but can continue on their current therapy or any other therapy as deemed appropriate by their physician.

Patients can then continue the therapy instituted beyond cycle 1 with any additional therapeutic agents as deemed appropriate by their physician and/or local physician.

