13.0 Treatment/Follow-up Decision at Evaluation of Patient

- 13.1 Off protocol treatment

Patients who go off protocol treatment before completing 6 cycles of treatment will not continue to be followed.
- 13.2 Criteria for Treatment Discontinuation

Patients may discontinue treatment for the following reasons:

 - Progressive multiple myeloma (see Section 11.0)
 - Patient withdraws consent to continue in the trial
 - Patient develops an intercurrent illness that precludes further participation, or requires a prohibited concomitant treatment
 - The Investigator withdraws the patient in the patient's best interests
 - Patient is lost to follow-up (defined as the inability to contact the patient on 3 separate occasions)
 - Administrative reasons (e.g., the patient is transferred to hospice care)
 - An adverse event, which in the opinion of the investigator precludes further trial participation

Patients will be taken off study if they discontinue treatments for any of the reasons above.

- 13.3 Criteria for Study Discontinuation

The study may be temporarily or permanently discontinued at any site and at any time. Reasons for study discontinuation may include, but are not limited to, the following:

 - Safety concerns
 - Non-compliance with the protocol, Good Clinical Practice guidance or other regulatory requirements by the Investigator(s)
 - Request to discontinue the trial by a regulatory or health authority or an IRB

- 134 Ineligible

A patient is deemed *ineligible* if after registration, it is determined that at the time of registration, the patient did not satisfy each and every eligibility criteria for study entry.

- If the patient received treatment, the patient may continue treatment at the discretion of the physician as long as there are not safety concerns. The patient will continue in the Active Monitoring/Treatment phase of the study, as per section 4.0 of the protocol.
- If the patient never received treatment, on-study material must be submitted. No further data submission is necessary.

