16.2 Statistical Design

Due to the lack of data to identify relevant biomarkers, the estimation of RR would be of interest. In each group, the response rates will be examined to see if there's any preliminary evidence to suggest further studies. This study will not utilize a formal statistical design.

For each biomarker category, the RR will be estimated by the number of patients who achieve a PR or better divided by the total number of evaluable patients in each cohort. Exact binomial 95% confidence intervals for these rates will be calculated.

16.22 Sample Size: A maximum of 30 evaluable patients will be accrued in cohort A and B and 60 patients in cohort C and D respectively. We anticipate accruing an additional 2 in cohort A and B and 3 in cohort C and D to account for ineligibility, cancellation, major treatment violation, or other reasons. Therefore, the maximum projected accrual is 190 patients (A: 32, B: 32, C: 63 and D: 63).

16.23 Accrual Rate and Study Duration: The anticipated accrual rate is 6 evaluable patients per month. Therefore, the accrual period for this pilot study is expected to be approximately 32 months. The final analysis can begin approximately 35 months after the trial begins, i.e. as soon as the last patient has been observed for 1 months and allowing 2 months for data entry.

16.24 Other considerations: Adverse events, quality/duration of response, and patterns of treatment failure observed in this study, as well as scientific discoveries or changes in standard care will be taken into account in any decision to terminate the study

16.3 Analysis Plan.

The analysis for this study is planned to start after data maturity has occurred. It is anticipated that the earliest date in which the result will be available via manuscript, abstract or presentation after the last registered patient has been followed for at least 1 month.

16.31 Primary Outcome Analyses:

Each cohort (A-D) will be evaluated separately and independently.

16.311 Definition:

The primary endpoint of this study is RR after 1 cycle of treatment. RR is defined as a binary variable. A success will be defined as patient who achieve a response of a PR or better using the IMWG criteria (Section 11.0) after one cycle of treatment. All patients meeting eligibility criteria who have signed a consent form, who complete at least one cycle of treatment and have successfully submitted biospecimens (pre and post treatment) will be evaluable for the endpoint.

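### The one-cycle response endpoint carries a two-determination confirmation rule, but only one determination is scheduled before cycle 2, so a value taken after cycle 2 treatment can decide who counts as a one-cycle responder

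*Combined protocol and SAP*

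**What the plan says.** Section 16.311 defines the primary endpoint: "A success will be defined as patient who achieve a response of a PR or better using the IMWG criteria (Section 11.0) after one cycle". It refers to Section 11.0 without exception. Evaluability is set in the same section: patients "who complete at least one cycle of treatment and have successfully submitted biospecimens (pre and post treatment) will be evaluable for the endpoint". A second response determination is not part of that definition.

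Section 11.2 requires serum M-protein, FLC and urine results to be verified on two consecutive determinations. Footnote a of Table 11.5 repeats the rule with a time limit: "All response categories require two consecutive assessments (sCR, CR, VGPR, PR, MR, PD) made at any time before the institution of any new therapy". It exempts bone marrow assessments. Section 11.1 reserves a value that qualifies only once for an unconfirmed category with internal uses, one of which is to guide test ordering.

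Section 4.0 schedules one post-baseline set of disease measurements before cycle 2. The later columns are before cycles 3-6 and End of Treatment. Section 7.1 lets standard of care agents be added in cycles 2-6.

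For progression only, footnote h says when confirmation may take place: "where the timing of confirmation is per the treating physician and can be done immediately within the same cycle or on the next cycle". There is no matching sentence for PR.

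**The concern.** Section 1.2 wants specimens before and after one cycle in which patients receive only an IMiD and dexamethasone, and the one-cycle response rate is meant to describe that exposure. If confirmation is required and the next scheduled value is taken after cycle 2, the label of one-cycle responder can depend on later treatment.

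Two analysts holding the same data could then report different response rates, depending on whether they count the single pre-cycle 2 value and on how they read *new therapy*. The same label feeds the biomarker regressions, the comparison of African American and white patients, and the depth-of-response analysis (16.321-16.323). If the choice is left until analysis, it will be made with results in view.

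**Working it through.** **The plan's own figures.** Evaluable 30 + 30 + 60 + 60 = 180; allowance 2 + 2 + 3 + 3 = 10; total 190. Accrual 190/6 = 31.7, stated as about 32 months; 32 + 1 + 2 = 35 months to final analysis. These reproduce.

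**When the determinations fall** (cycle lengths from 7.1, windows from 4.0), in days from treatment start:
- Before cycle 2: 21 ± 3, so days 18-24.
- Before cycle 3: 21 + 28 = 49 ± 3, so days 46-52.
- Added agents are allowed from the start of cycle 2, between these two.

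**What happens to a patient who meets PR before cycle 2.**
1. *Added agents are protocol treatment, not new therapy.* The pre-cycle 3 value, possibly taken on an added drug, decides confirmation.
2. *An added agent is new therapy.* Without an unscheduled repeat test before the agent starts, the response cannot be confirmed. Under 16.311 the patient stays in the denominator and counts as a failure.
3. *The patient stops after cycle 1.* The End of Treatment visit supplies the second determination, unless it is the same draw as pre-cycle 2. After that, "Patients who go off protocol treatment before completing 6 cycles of treatment will not continue to be followed".

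For the same patients the order is fixed: single determination ≥ confirmed with added agents allowed ≥ confirmed before any added agent. Each set of responders is contained in the one before it.

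**Which reading of new therapy the text favours.** The tables for cycles 2-6 sit under Protocol Treatment, and those patients remain on study. Note 4 of Section 4.0 lists "patient refusal, subsequent treatment for myeloma" among the reasons for discontinuing, which separates it from such additions. Against this, 7.3 says "Patients can then continue the therapy instituted beyond cycle 1 with any additional therapeutic agents as deemed appropriate", but that follows a sentence about patients having left the study. Reading 1 is the better supported.

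**Size.** If k one-cycle responders are not confirmed, the response rate falls by k/n. For k = 1 this is 1/30 = 3.3 points or 1/60 = 1.7 points. The documents give neither k nor an expected one-cycle rate, so rates of 20, 40 and 60% are assumed. The exact (Clopper-Pearson) limits are the 0.025 quantile of Beta(x, n − x + 1) and the 0.975 quantile of Beta(x + 1, n − x).

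| x/n | Rate | 95% CI | Half-width | Shift for k = 1 ÷ half-width |
|---|---|---|---|---|
| 6/30 | 20% | 7.7-38.6 | 15.4 | 21.6% |
| 12/30 | 40% | 22.7-59.4 | 18.4 | 18.1% |
| 18/30 | 60% | 40.6-77.3 | 18.4 | 18.1% |
| 12/60 | 20% | 10.8-32.3 | 10.8 | 15.5% |
| 24/60 | 40% | 27.6-53.5 | 12.9 | 12.9% |
| 36/60 | 60% | 46.5-72.4 | 12.9 | 12.9% |

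Ratios use unrounded half-widths.

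**The case against.** The strongest reply is that a single reading is plainly intended. The endpoint is worded as after one cycle. Section 13.5 ties evaluability to cycle 1 treatment. Section 16.23 starts the final analysis "as soon as the last patient has been observed for 1 months and allowing 2 months for data entry". Counted from treatment start, one month (30.4 days) covers days 18-24 but not days 46-52. This stands as evidence of intent, with a limit: 16.23 does not say where the month starts. Counted from registration, with treatment starting up to 28 days later (6.5), even the pre-cycle 2 value can fall at 28 + 24 = day 52. No passage lifts the confirmation rule for this endpoint.

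It can also be said that footnote a sets no minimum interval, so a repeat before cycle 2 is already allowed and the unconfirmed label may prompt one. That is true, but the repeat is neither scheduled nor required.

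Three stronger inferences are tempting and not supported:
- *Any added agent voids the response.* This needs the weaker reading of *new therapy*.
- *Stopping after cycle 1 loses the response.* Section 4.0 has a separate End of Treatment column with the disease measurements, and nothing says it is the same draw as pre-cycle 2.
- *The response rate moves by 10 points.* That takes k = 3 at n = 30 or k = 6 at n = 60. It would be 54-65% and 77-93% of the half-width, but at a 20% rate it means half of all responders going unconfirmed (3 of 6, 6 of 12), and at 40% a quarter. Nothing in the documents points to losses of that size.

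Finally, this is an estimation-only pilot with no response threshold. That limits the consequence, but the estimate is the study's main product.

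**Conclusion.** The point holds as a gap in the definition of the primary endpoint. Following the plan literally, the second determination comes from after cycle 2 unless someone orders an extra test or, for a patient who stops, the End of Treatment visit supplies it. On the better-supported reading, a value taken after cycle 2, possibly on an added drug, decides whether a one-cycle response is confirmed. On the weaker reading, some responders cannot be confirmed but stay in the denominator.

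The cost per unconfirmed responder is 3.3 points in cohorts A and B and 1.7 points in C and D. The comparison with the interval width rests on the assumed rates of 20-60%. The number of such patients is unknown and may be zero. Patients measurable only by marrow are unaffected. The effect is on the response-rate estimate and on the responder label in 16.321-16.323; no go/no-go rule changes. It should be settled before the data are analysed.

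**What to change.** In 16.311, write:

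> Success is meeting the Table 11.5 criteria for PR or better at the Prior to Day 1 Cycle 2 assessment, drawn before any added agent is given. Footnote a's imaging condition (no known new or progressing bone lesion or extramedullary plasmacytoma) still applies. The two-assessment confirmation requirement does not apply to this fixed-time endpoint.

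Three additions go with it:
- State how patients measurable only by imaging are scored when no imaging is done at that visit, and report their number. Such patients are eligible under 11.1, but post-baseline imaging in 4.0 is done only if clinically indicated.
- In footnote a, state whether an agent added in cycles 2-6 is *new therapy*, for response scoring only.
- As a sensitivity analysis, report confirmed PR using only assessments made before any added agent, with the number of responders not confirmed and the reason.

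The cost is a few sentences and one extra analysis. Sample size is unchanged, and the primary analysis does not have to wait for the pre-cycle 3 value. The downside is that a single determination carries somewhat more measurement noise, which the documents do not allow to be quantified.
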